9.2.2. Study Data

Study data identified in this protocol are collected, and source verified, on electronic Case Report Forms (eCRF) at sites completing the study. All study data will be formulated into data sets to provide transparency, traceability, and integrity of trial analysis results from collection source. Observed study data will be mapped to the Clinical Data Interchange Standards Consortium (CDISC) Study Data Tabulation Model (SDTM) and serve as the source data from the trial. All study analyses will be completed using analysis data sets that are derived from the SDTM and follow the CDISC Analysis Data Model (ADaM) architecture.

9.2.2.1. Clinical Data – CDISC Study Data Tabulation Model (SDTM)

Domains will be mapped to CDISC SDTM using implementation guide version 3.2. No derived data required for analysis are included in the SDTM domains. All SDTM domains will be fully documented with define documents (DEFINE.XML) and a Study Data Reviewer's Guide (SDRG) after database lock and final analyses are completed.

9.2.2.2. Analysis Data – CDISC Analysis Data Model (ADaM)

All planned and exploratory analyses will be completed using CDISC compliant ADaM data sets derived from the SDTM domains for this study. Analysis data sets will contain all derived study endpoints required for analysis. All ADaM analysis data sets will be fully documented with define documents (DEFINE.XML) and an Analysis Data Reviewer's Guide (ADRG) after database lock and final analyses are completed.

9.2.3. Study Endpoints for Assessment

The same endpoints for Part I and the double-blind phase of Part II of the study will be used. However, all endpoints will be exploratory in Part I of the study.

CONFIDENTIAL Page 62 of 72

9.2.3.1. Key Primary Efficacy Endpoint

• Change from Baseline on the WOMAC A (pain) score at Week 12

9.2.3.2. Key Secondary Efficacy Endpoints

- Change from Baseline on the WOMAC C (function) score at Week 12
- PGIC score at Week 12

9.2.3.3. Additional Secondary Efficacy Endpoints:

- Area Under the Effect curve (AUE) of change from Baseline on the WOMAC A (pain) subscale over the time intervals (e.g., Weeks 1 to 4, Weeks 1 to 8, and Weeks 1 to 12)
- AUE of change from Baseline on the WOMAC C (function) score over the time intervals (e.g., Weeks 1 to 4, Weeks 1 to 8, and Weeks 1 to 12)
- PGIC at Weeks 1, 4, and 8
- Change from Baseline on the WOMAC A (pain) score at Weeks 1, 4, and 8
- Change from Baseline on the WOMAC C (function) score at Weeks 1, 4, and 8
- Change from Baseline on the WOMAC B (stiffness) score at Weeks 1, 4, 8, and 12
- Change from Baseline on the WOMAC total score at Weeks 1, 4, 8, and 12
- Percent of responders (defined as patients with high improvement in pain or function) according to OMERACT-OARSI criteria at Weeks 1, 4, 8, and 12
- Proportion of patients experiencing a ≥20%, ≥30%, or ≥50% decrease in WOMAC A
 (pain) at Weeks 1, 4, 8, and 12
- Rescue medication use at Weeks 1, 4, 8, 12 and total consumption
- Change from Baseline on the SI at Weeks 1, 4, 8, and 12
- Change from Baseline on the EQ-5D-5L at Weeks 1, 4, 8, and 12
- Change from Baseline on the HOOS-QOL at Weeks 1, 4, 8, and 12
- TSOM-9 at Week 12
- Change from Baseline on WOMAC A (pain), B (stiffness), C (function) and PGIC at Weeks 1, 4, 8, and 12 in patients with unilateral hip OA

The same endpoints as above will be examined post Week 12 during the OLE phase of Part II with the addition of the following:

• Time to second injection for patients who receive a second injection of FX006

CONFIDENTIAL Page 63 of 72

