7. INVESTIGATIONAL PLAN

7.1. Overall Study Design and Plan

This is a two-part, multi-center, randomized, double-blind, placebo-controlled, parallel-group study in patients with hip OA. Approximately 70 patients will be enrolled in Part I and approximately 440 patients will be enrolled in Part II of the study. In each part, patients will be randomized to one of two treatment groups (1:1) and treated with a single IA injection of either 32 mg FX006 or normal saline.

Eligible patients will be randomized within strata defined by Baseline Western Ontario and McMaster Universities Osteoarthritis Index (WOMAC) A (pain) (0-10 numeric ratings scale (NRS) average of Screening 2 and Day 1 with the following classifications: 5.0 to < 6.0, 6.0 to < 7.0, and $\geq 7.0 \text{ to} 9.0$ (see Section 9 for details).

FX006 or saline placebo will be administered as a single IA injection with a 12-week follow-up period in the double-blind phase.

Patients participating in Part I of the study will be treated with a single IA injection of either 32 mg FX006 or normal saline and will return for follow up visits at Weeks 12, 16, 20, and 24 or up until the time of this amendment. The patients will be discontinued at the time of notification by the Investigator.

Patients participating in Part II of the study will be treated with a single IA injection of either 32 mg FX006 or normal saline and will return for follow up visits at Weeks 12, 16, 20, and 24. Patients who are eligible for the second injection in the open-label phase at Week 12 will receive an open-label injection of FX006 at Week 12 and return for follow-up visits at Weeks 16, 20, and 24. These patients will complete the study at Week 24.

Patients participating in Part II of the study that are not clinically indicated for a second injection at Week 12 will return to the clinic at Weeks 16, 20, and 24 and will receive an open-label injection of FX006 at the first evaluation where the patient has been determined to meet all criteria. Patients will then return for follow-up visits every 4 weeks for 12 weeks post second injection and will complete the study 12 weeks post second injection (e.g., Week 24, 28, 32, or 36 depending on when the patient receives the open-label injection).

Patients participating in Part II of the study who are not eligible for a second injection after evaluation at Weeks 12, 16, 20, and 24 will complete the study at the Week 24 visit and complete the End of Study (EOS) assessments.

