7.4.4. Second Injection Inclusion Criteria (Part II Patients Only)

To be eligible to receive the second injection during the open-label phase, patients must fulfill the following criteria:

- 1. Completed the double-blind phase of the study through Week 12
- 2. No major safety concerns during the initial dose period (including allergic reaction to initial dose of study medication) as assessed by the Investigator and patient
- 3. Clinically indicated to receive FX006, in the opinion of the Investigator and patient
- 4. WOMAC A (pain) score of ≥ 3 (0-10 NRS)
- 5. Compliant with study procedures and visit schedules up to the open-label injection with FX006 and the willingness and ability to continue to comply for additional 12 weeks after the second injection
- 6. Willingness to continue abstaining from use of protocol-restricted medications during the study (Refer to Section 7.6.2)

CONFIDENTIAL Page 37 of 72

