9.2.1. Analysis Populations

The following analysis populations are planned for each part of this study as follows:

- Full Analysis Set (FAS) Population: All patients who received study drug. The FAS population will be used to examine efficacy endpoints for the double-blind phase of the study
- Safety Population: All subjects who received at least one dose of study drug. The Safety Population will be used to assess safety and tolerability
- Second Injection Population (Part II only): All patients who received a second injection. The Second Injection Population will be used to examine efficacy endpoints in the openlabel extension phase of the study
- Per Protocol Population (Part II Only): All patients in the FAS population who completed the Week 12 visit with no major protocol deviations that may impact the evaluation of the primary efficacy endpoint based on blinded data prior to unblinding of the double-blind phase data.

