9.4.2. Exposure

Treatment exposure will be listed by study site and subject, and will be summarized by treatment and dose. The number of doses administered as well as total exposure will be summarized. Time between first and second injections will also be summarized.

CONFIDENTIAL Page 64 of 72

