9.4.3. Efficacy Analyses

Primary Efficacy Analysis

The primary endpoint will be analyzed with a longitudinal mixed model for repeated measures (MMRM) with fixed effects for treatment group, study week, treatment-by-week interaction and Baseline score. Subject will be the random effect. Treatment differences from control will be estimated via least square means from the analysis model along with 95% confidence intervals, and associated 2-sided p-values. This model assumes missing at random and includes only observed data.

Secondary Efficacy Analyses

Key secondary endpoints will be assessed similarly to the primary endpoint. Multiplicity will be addressed by analyzing the key secondary endpoints sequentially in the order presented in the protocol, testing each endpoint at the nominal alpha=0.05, 2-sided level to ensure overall type I error control at the 2-sided 0.05 level.

Additional continuous secondary efficacy endpoints will also be assessed similarly to the primary endpoint, but are not part of the sequential testing approach. Categorical end points will be compared via chi-square or exact tests depending on incidence rates.

AUE will be calculated and comparisons of the AUE endpoints will be estimated from an Analysis of Covariance (ANCOVA) with model parameters for treatment and covariates of Baseline WOMAC A score and study site. Full details of the AUE analyses will be detailed in the SAP.

Efficacy Analyses For The Open-Label Extension Phase (Part II)

Exploratory efficacy endpoints for the open-label extension phase will be analyzed similarly to the primary and secondary endpoints, but separately for the time period prior to the second injection and the time period post the second injection. Time-to-event endpoints will be assessed via log-rank tests and results will be presented in Kaplan-Meier plots.

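### Time to second injection is defined only in patients who receive one, so the planned log-rank and Kaplan-Meier analysis has no censoring and ignores the share re-injected

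*Protocol*

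**What the plan says.** Protocol 9.2.3.3 carries the double-blind endpoints into the OLE phase of Part II and adds one: "Time to second injection for patients who receive a second injection of FX006". It is the only time-to-event endpoint in the list.

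Protocol 9.2.1 defines the Second Injection Population as the Part II patients who had a second injection and gives it the OLE efficacy work: "The Second Injection Population will be used to examine efficacy endpoints" in that phase.

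Protocol 9.4.3 states the method: "Time-to-event endpoints will be assessed via log-rank tests and results will be presented in Kaplan-Meier plots". It gives no censoring rule and names no comparison groups. The same paragraph sets the status: "Exploratory efficacy endpoints for the open-label extension phase will be analyzed similarly to the primary and secondary endpoints".

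Protocol 7.1 foresees Part II patients who never have the event, those "who are not eligible for a second injection after evaluation at Weeks 12, 16, 20, and 24 will complete the study" at Week 24. Under 7.4.4, re-injection requires a WOMAC A score of at least 3 and also that the patient be "Clinically indicated to receive FX006, in the opinion of the Investigator and patient".

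Protocol 9.4.2 covers exposure descriptively: "The number of doses administered as well as total exposure will be summarized", along with the interval between the two injections.

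Protocol 9.4 leaves full analysis detail to a separate Part II SAP. The SAP supplied covers Part I only.

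**The concern.** The endpoint wording, the population and the method together condition on the event. A Kaplan-Meier curve is meant to show how many patients are still free of the event. Here only patients who have the event enter, so the curve can describe nothing but when, among recipients, the injection was given. Patients who were assessed four times and never re-injected are the natural censored observations, and they are missing.

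Membership of the analysed set is decided after randomization and depends on outcome, through the pain threshold and the judgement that treatment is indicated. A log-rank test between arms inside that set is not a randomized comparison.

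The practical risk is that a published p-value and plot are read as evidence on how long patients go before re-injection, although they omit those who completed follow-up without one.

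**Working it through.** The plan gives no power, event count or re-injection rate for this endpoint, so there is no figure of its own to reproduce.

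**What follows from the wording alone.** Let p be the share re-injected and F(t) the distribution of injection time among recipients, with possible times Weeks 12, 16, 20 and 24.
- Recipients only: injection-free at t = 1 − F(t). This does not contain p and is 0 at Week 24.
- All patients evaluated, with the others censored at Week 24: injection-free at t = 1 − p·F(t), which ends at 1 − p.

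For example, with timing 55/20/15/10% over the four visits (an assumption), the recipients-only curve is 45%, 25%, 10%, 0% for every p. The all-patient curve ends at 60% for p = 0.4 and at 20% for p = 0.8.

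The log-rank statistic is (ΣO − ΣE)²/ΣV, with E = d·n₁/n and V = d·(n₁/n)(1 − n₁/n)(n − d)/(n − 1) at each visit. Among recipients, everyone still at risk at Week 24 is injected then. So d = n, O = E = n₁ and V = 0, and the test rests on Weeks 12, 16 and 20 alone.

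**Size, by simulation.** From the documents: 220 per arm, 6% early discontinuation (9.3.1), four evaluation visits, two-sided 0.05. Assumed: the comparison is between randomized arms, all discontinuation falls before Week 12, a fraction c never needs re-injection, and each remaining patient is re-injected with probability h at each visit. Then

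share re-injected = 0.94 × (1 − c) × [1 − (1 − h)⁴].

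With c = 0.15 and h = 0.6 this is 0.94 × 0.85 × 0.9744 = 78%. With c = 0.25 it is 69%.

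The table gives the percentage of trials significant (5000 trials per row; 3000 for the softened case). Arms are placebo v FX006.

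| Scenario | Share re-injected | All treated, censored | Recipients only |
|---|---|---|---|
| A: h 0.6 both; c 0.15 v 0.20 | 78% v 73% | 22% | 5–6% |
| A: c 0.15 v 0.25 | 78% v 69% | 64% | 5–6% |
| A: c 0.15 v 0.30 | 78% v 64% | 92% | 5–6% |
| A: c 0.15 v 0.35 | 78% v 60% | 99% | 5–6% |
| A: h 0.3 both; same four values of c | 61% v 57, 54, 50, 46% | 12, 34, 63, 86% | 5% |
| B: c 0; h 0.35 v 0.25 | 77% v 64% | 94% | 26% |
| B: c 0; h 0.25 v 0.18 | 64% v 51.5% | 84% | about 12% |
| C: c 0.15 v 0.30; h 0.5 v 0.65 | 75% v 65% | 37%, all for FX006 | 75%, all against FX006 |
| C: c 0.15 v 0.35; h 0.5 v 0.7 | 75% v 61% | 69% for FX006 | 94% against FX006 |
| C softened: c 0.15 v 0.30; h 0.5 v 0.55 | 75% v 63% | 70% for FX006 | 12% against FX006 |
| D: c 0.15 both; h 0.6 v 0.5 | 78% v 75% | 29% | 42% |
| D: c 0.15 both; h 0.6 v 0.45 | 78% v 73% | 63% | 74% |

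With no difference between arms (c = 0.25 in both), both tests reject in about 5%. In the first C row the mean time among recipients is 14.9 v 13.9 weeks.

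A second simulation used 206 completers per arm (220 × 0.94, rounded down), the 55/20/15/10% timing in both arms, and 2000 trials. At 70% v 60% re-injected the all-patient test rejects in 55% and the recipients-only test in 5%. At 70% v 50% the figures are 99% and 5%. With 70% re-injected in both arms but later timing on FX006 (35/25/22/18%), the order reverses: 18% for all patients, 88% for recipients only.

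**The case against.** The strongest objection is that the risk set, censoring rule and comparison groups are ordinary SAP content, and the Part II SAP is not available. No sentence says that nobody is censored; that comes from joining 9.2.3.3, 9.2.1 and 9.4.3. This is fair as far as it goes, and a Part II SAP could still put it right. But the restriction to recipients is written into the endpoint and repeated in the population, so a SAP that follows the protocol would carry it forward. The log-rank sentence has no other listed endpoint to apply to.

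Second, the OLE objectives concern safety and efficacy after the second injection, not durability of the first, and the comparison between arms is assumed. This stands as a limit on the simulated figures. The lack of censoring does not depend on it.

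Third, the figures depend on assumed rates. Scenario A gives 5% by construction, the reversed direction in C largely disappears when the timing difference is softened, and in D the recipients-only test has more power. All of this stands. The defect is that the share re-injected is ignored, not that power is lost in every case.

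Fourth, patients without a second injection are not all doing well. Some are barred for safety, for not being "Compliant with study procedures and visit schedules up to the open-label injection with FX006", or under 7.4.5. This is correct, and the fix has to deal with them.

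Finally, the dose counts in 9.4.2 would probably show a difference in the share re-injected. That helps the reader of the report but does not repair the test or the plot.

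**Conclusion.** The concern holds. As specified, the analysis has no censored observations, its curve must reach zero by Week 24, and neither curve nor test responds to the share of patients re-injected. That much follows from the protocol's wording.

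The consequence is sized only under assumed rates and a comparison between randomized arms. With equal timing among recipients, a difference of 5 to 18 percentage points in the share re-injected (78% v 73% to 60%) goes undetected beyond the error level, where a censored analysis would find it in 22% to 99% of trials. When recipients in the arm with fewer re-injections are also markedly earlier, the result can point the wrong way. When only timing differs, the recipients-only test can be the more powerful.

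The importance is limited. This is one exploratory OLE endpoint, with no bearing on the primary or key secondary conclusions or on the sample size. It is a cheap correction worth making before Part II is analysed.

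**What to change.** - **Protocol 9.2.3.3:** define the endpoint as time from Day 1 to second injection in all treated Part II patients, by randomized first treatment. Censor patients without a second injection at their last second-injection evaluation (Week 24) or at earlier discontinuation.
- **Protocol 9.2.1:** except this endpoint from the Second Injection Population. If the Full Analysis Set is named, use the 9.2.1 definition. The synopsis version also requires baseline and post-dose pain data, and 9.2.1 assigns the set to the double-blind phase, so both points need a word.
- **Protocol 9.4.3 and the Part II SAP:** state the comparison groups and the censoring rule, and report the proportion re-injected by Week 24 by arm with a 95% CI. With only four tied event times, a discrete-time log-rank test or complementary log-log model, stratified by the three WOMAC A strata, would be suitable.
- **Part II SAP:** say how patients barred under 7.4.4 or 7.4.5 for reasons other than pain relief are handled, for example as a competing event in a sensitivity analysis.
- **Label:** call it time to re-injection, not duration of effect, because the event depends partly on investigator and patient opinion. Keep the recipients-only interval as the descriptive summary already planned in 9.4.2.

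The cost is one sentence in each of the three protocol sections and a paragraph in the Part II SAP. Injection dates, evaluation visits and the second-injection criteria are already collected.

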9.2.4. Sub-Groups and Covariates

Other pre-planned sub-groups analyses per aspiration status, KL grade, gender and the baseline pain score, etc. will be detailed in the SAP. Sub-groups (e.g., second dose cohorts (Week 12, 16, 20, or 24)) may be defined and explored after all pre-planned analyses have been completed to further elucidate study results.

Covariates for efficacy analyses will include baseline WOMAC A score, baseline score for the endpoint and study site. Other covariates may be explored and will be fully defined in the SAP.

9.3. Determination of Sample Size

9.3.1. Sample Size Considerations

Approximately 70 patients will be randomized in Part I and approximately 440 patients will be randomized in Part II in this study (an estimated 35 and 220 per treatment group respectively.)

For Part I, a sample size of approximately 35 per arm will provide information regarding the treatment effect. For Part II of the study, the expected sample size was determined based on the primary endpoint as follows. A minimum sample size of N=212 per arm for the placebo and the FX006 group has 90% power to yield a statistically significant difference (alpha=0.05, 2-sided) if the true underlying difference at Week 12 is 0.65 and with an assumption of 2.0 for the SD. For the first key secondary endpoint, the sample size of N=220 per treatment group has 90% power to yield a statistically significant difference between FX006 and placebo if the true underlying difference is 0.68 at Week 12, assuming a SD of 2.125. An early discontinuation rate of 6% was assumed. The data from Part I may be used to inform if the above assumptions were appropriate and the planned sample size for Part II should remain at 440, or whether a smaller sample size would be feasible.

9.4. General Statistical Methods

Complete details of the statistical analysis will be specified in the SAP. A separate SAP will be prepared for Part I and Part II of the study prior to database lock for each part of the study. Parts I and II of the study will enroll separate patients, and as such all analyses will be performed independently of one another. Analyses for Parts I and II of the study will be performed in the same manner, as detailed below. The analyses of the Part I data will be performed in an unblinded manner and results may be used to inform the conduct of Part II; as the analyses of Part I will be completed prior to the enrollment of any patients in Part II, this will have no impact on maintaining the blind for Part II. All analyses of Part I data are exploratory in nature.

9.4.1. Demographics and Baseline Characteristics

Demographic and baseline characteristics will be listed by study site and subject, and will be summarized by treatment. Frequencies and proportions will be presented for the categorical variables and descriptive statistics will be presented for continuous variables.

9.4.2. Exposure

Treatment exposure will be listed by study site and subject, and will be summarized by treatment and dose. The number of doses administered as well as total exposure will be summarized. Time between first and second injections will also be summarized.

CONFIDENTIAL Page 64 of 72

9.4.3. Efficacy Analyses

Primary Efficacy Analysis

The primary endpoint will be analyzed with a longitudinal mixed model for repeated measures (MMRM) with fixed effects for treatment group, study week, treatment-by-week interaction and Baseline score. Subject will be the random effect. Treatment differences from control will be estimated via least square means from the analysis model along with 95% confidence intervals, and associated 2-sided p-values. This model assumes missing at random and includes only observed data.

Secondary Efficacy Analyses

Key secondary endpoints will be assessed similarly to the primary endpoint. Multiplicity will be addressed by analyzing the key secondary endpoints sequentially in the order presented in the protocol, testing each endpoint at the nominal alpha=0.05, 2-sided level to ensure overall type I error control at the 2-sided 0.05 level.

Additional continuous secondary efficacy endpoints will also be assessed similarly to the primary endpoint, but are not part of the sequential testing approach. Categorical end points will be compared via chi-square or exact tests depending on incidence rates.

AUE will be calculated and comparisons of the AUE endpoints will be estimated from an Analysis of Covariance (ANCOVA) with model parameters for treatment and covariates of Baseline WOMAC A score and study site. Full details of the AUE analyses will be detailed in the SAP.

Efficacy Analyses For The Open-Label Extension Phase (Part II)

Exploratory efficacy endpoints for the open-label extension phase will be analyzed similarly to the primary and secondary endpoints, but separately for the time period prior to the second injection and the time period post the second injection. Time-to-event endpoints will be assessed via log-rank tests and results will be presented in Kaplan-Meier plots.

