5.2.6. Efficacy in Patients with Osteoarthritis of the Knee

Efficacy data from three studies provide substantial evidence supporting the effectiveness of 32 mg FX006 in the management of OA pain (Bodick et al, 2015; Conaghan et al, 2018a; Conaghan et al, 2018b). Results of the primary endpoint from the Phase 3, multi-center, adequate, and well-controlled trial showed that patients treated with 32 mg FX006 had a rapid, durable, and meaningful analgesic response that was statistically significantly better than placebo treated patients (P<0.0001). This finding was supported by a second smaller Phase 2b study, where a highly similar pattern of response to 32 mg FX006 was demonstrated.

Robustness of the primary outcome in the Phase 3 study was further supported by the internal consistency demonstrated in favor of 32 mg FX006 through secondary analyses utilizing the primary outcome data (average daily pain [ADP]) to evaluate durability and magnitude of response. These included least square mean (LSM) testing at each week and area under the

CONFIDENTIAL Page 25 of 72

effect curve (AUE) analyses for Weeks 1 through 12 and Weeks 1 through 24. Results demonstrated that the analgesic effect of 32 mg FX006 is significant at Week 1, increases through Week 7, and is sustained through at least Week 16. Responder analyses further suggested that FX006 provides clinically relevant improvement from Weeks 1 through 16 relative to placebo.

Analyses utilizing data collected from other instruments or measures, i.e., Western Ontario and McMaster Universities Osteoarthritis Index (WOMAC), Patients' Global Impression of Change (PGIC), Clinical Global Impression of Change (CGIC), and Knee injury and Osteoarthritis Outcome Score (KOOS) Quality of Life (QOL), provided additional insight into effects on pain relief as well as physical function and global well-being. At 32 mg, FX006 provides clinically relevant improvement relative to placebo through Week 12 for WOMAC and KOOS QOL and through at least Week 16 for PGIC and CGIC. Additionally, significant reduction of rescue medication utilization in patients treated with 32 mg FX006 is of potential important clinical consequence and adds a meaningful element to the overall effectiveness profile of 32 mg FX006. Collectively, these results provide substantial evidence to support 32 mg FX006 as an effective therapy for the management of OA knee pain.

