6.3. Open Label Phase Objectives

6.3.1. Secondary Objective:

To examine efficacy following a second injection of FX006 in patients with hip OA

6.3.2. Primary Objective:

• To assess the overall safety of a second injection of FX006 in patients with hip OA

CONFIDENTIAL Page 29 of 72

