#### **4.2.10. Baseline definitions**

Baseline is the Baseline/Day 1 assessment prior to administration of the first dose of study treatment. If the Baseline result is missing, the last non-missing result prior to administration of study treatment may be used from the screening period.

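### The open-label efficacy analysis sets no reference value at the second injection and has no control arm, so improvement already present at re-injection can be counted as its result

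*Protocol*

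**What the plan says.** The secondary objective of the open-label phase (Protocol 6.3) is: "To examine efficacy following a second injection of FX006 in patients with hip OA".

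The endpoints come from the double-blind list. Protocol 9.2.3.3 states: "The same endpoints as above will be examined post Week 12 during the OLE phase of Part II", and adds only time to second injection. Most of that list is change from Baseline, or a 20%, 30% or 50% decrease in WOMAC A.

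Protocol 9.4.3 calls the open-label efficacy endpoints exploratory and analyses them like the primary and secondary endpoints, "but separately for the time period prior to the second injection and the time period post the second injection". The primary model in that section estimates treatment differences from control.

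No section defines a baseline before the second injection. The SAP (4.2.10) states: "Baseline is the Baseline/Day 1 assessment prior to administration of the first dose of study treatment"; SAP 4.10.1.1 repeats this for WOMAC. That SAP covers Part I only (SAP 1.2 and 4.4). Protocol 9.4 promises a separate Part II SAP, which is not among the documents.

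**The concern.** The objective asks what happens after a second injection. A change measured from before the first injection mixes that with everything since Day 1. In patients first given FX006, this includes any remaining effect of the first dose. In patients first given saline, it includes placebo response, natural course and regression to the mean. To the extent that such improvement persists, it is counted as improvement after the second injection.

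The between-arm comparison has a separate problem. Everyone in the Second Injection Population (Protocol 9.2.1) receives open-label FX006, so no arm is a control for the second injection. A model like the primary would compare a repeat exposure with a first exposure, in patients selected partly by their response so far. At stake is whether the open-label efficacy tables answer the stated objective.

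**Working it through.** **The plan's own figure.** The documents give no figure for the open-label efficacy analysis. The planning difference and SD used below come from Protocol 9.3.1: "A minimum sample size of N=212 per arm for the placebo and the FX006 group has 90% power", "if the true underlying difference at Week 12 is 0.65 and with an assumption of 2.0 for the SD". The check is n = 2(1.960 + 1.282)² × 2.0² / 0.65², about 199 evaluable per arm, and 199 / (1 - 0.06) = 211.7, so 212. The figure reproduces. It does not bear on this point except as a source of inputs.

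**Arithmetic from the eligibility limits.** Entry WOMAC A is 5.0 to 9.0 (Protocol 7.4.2); re-injection requires at least 3 (7.4.4). For a patient re-injected at exactly 3, improvement from Day 1 score b is (b - 3)/b:

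| Day 1 score | Change at re-injection | Improvement |
|---|---|---|
| 5 | -2 | 40% |
| 6 | -3 | 50% |
| 7 | -4 | 57% |
| 8 | -5 | 62.5% |
| 9 | -6 | 67% |

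Such a patient meets the 30% criterion from any eligible entry score, and the 50% criterion from 6 upward, before the second injection is given. The 30% criterion is already met at any re-injection score up to 0.7b: 3.5 for entry at 5, and 6.3 for entry at 9. In the other direction, a patient at or above the Day 1 level at re-injection carries nothing forward. The possible change at re-injection runs from -6 (9 to 3) to +5 (5 to 10).

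**Simulation with a null second injection** (400,000 patients per arm).

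- From the documents: SD 2.0, first-injection effect 0.65, re-injection only if WOMAC A is at least 3.
- Assumed: Day 1 score uniform on 5 to 9; saline-arm mean change to Week 12 of -1, -2 or -3; correlation 0.7 between Week 12 and Week 24 deviations; scores kept within 0 to 10; 100%, 50% or 0% of the mean improvement retained 12 weeks after a Week 12 re-injection.

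Results for the arm first given FX006, in the order of assumed saline-arm change -1 / -2 / -3:

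| Improvement retained | Mean change from Day 1 | At least 30% decrease from Day 1 | Mean change from pre-second-injection value |
|---|---|---|---|
| All | -1.32 / -2.09 / -2.81 | 33% / 49% / 64% | -0.15 / -0.24 / -0.36 |
| Half | -0.53 / -0.80 / -1.01 | 18% / 21% / 24% | +0.64 / +1.05 / +1.43 |
| None | +0.22 / +0.42 / +0.66 | 9% / 6% / 3% | +1.40 / +2.27 / +3.11 |

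With full retention, the small remaining change from the pre-second-injection value is regression to the mean created by the 3-point threshold. With half retention the two references disagree in sign: the Day 1 reference shows benefit while patients are getting worse.

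**Between-arm contrast** (FX006-FX006 minus saline-FX006), same order, true second-injection effect zero:

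| Improvement retained | From Day 1 | From pre-second-injection value |
|---|---|---|
| All | -0.52 / -0.49 / -0.46 | -0.05 / -0.06 / -0.08 |
| Half | -0.20 / -0.17 / -0.13 | +0.27 / +0.25 / +0.25 |
| None | +0.11 / +0.13 / +0.16 | +0.58 / +0.56 / +0.54 |

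The contrast follows the persistence or waning of the first injection, whichever reference is used. The arms also differ in who is re-injected: with full retention, 84% / 72% / 56% of the FX006 arm against 90% / 81% / 67% of the saline arm reach the threshold.

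**The case against.** The strongest reply is that Day 1 as the open-label baseline is an inference. Its definition sits in a SAP for Part I, where no second injection is planned, and the Part II SAP may set another. This stands, and a reader who concludes that the plan settles on Day 1 goes further than the documents. Protocol 9.1 and 9.4 do say that both parts will be analysed in the same manner, and the baseline used for stratification (the Screening 2 and Day 1 average, 7.1) also precedes the first dose. On the narrowest reading the reference is undefined, which calls for the same correction.

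A reader might also infer that the inherited improvement is first-injection drug effect. That can hold only in the arm first given FX006. The support is weaker than it looks: the Protocol 5.2.6 statement that the effect "is significant at Week 1, increases through Week 7, and is sustained through at least Week 16" concerns average daily pain in the knee. The same section gives WOMAC benefit over placebo only through Week 12, the earliest re-injection visit.

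Finally, a reader might infer that an inert second injection would always look effective. It would not: the false benefit shrinks as improvement fades and is absent with no retention. Criterion 3 in 7.4.4, that re-injection be judged clinically indicated, plausibly selects patients whose relief has faded, and the simulation leaves it out.

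It is also fair that the endpoints are exploratory, that the primary open-label objective is safety, that the period before re-injection is reported separately so part of the inherited change is visible, and that change from Day 1 is a legitimate description of benefit under repeat dosing. None of this gives the period after re-injection its own reference or a control.

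**Conclusion.** The point holds in a limited form. As written, the protocol applies change-from-Baseline and percent-decrease endpoints after the second injection without a pre-second-injection reference, and points to a treatment-versus-control model where no control exists. That method does not answer the objective in 6.3.

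The threshold arithmetic (40% to 67% improvement already present at a re-injection score of 3) rests only on the protocol's limits and the Day 1 reading. The average size is conditional. For a null second injection in the arm first given FX006, it is about -1.3 to -2.8 points with full retention and -0.5 to -1.0 with half, with no false benefit if none is retained. These ranges depend on the assumed Day 1 distribution, saline-arm response, correlation and retention, none of which the documents give.

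The primary and key secondary tests at Week 12 and their type I error are unaffected. This should be corrected in the Part II SAP, but it does not threaten the trial's main conclusion.

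**What to change.** Amend Protocol 9.2.3.3 and 9.4.3 and specify in the Part II SAP, before the unblinded Part II analysis described in 9.1.1:

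- Add the last value before the second injection as the reference for change and percent-decrease endpoints after it, for WOMAC, SI, HOOS-QOL and EQ-5D-5L. Table 7-3 schedules all four at the second-injection visit, with questionnaires before other assessments.
- Do not re-base PGIC or the PGIC component of OMERACT-OARSI. SAP 4.10.3 describes PGIC as asking how the patient feels relative to Baseline. State which reference the composite uses.
- Report within-cohort estimates with confidence intervals, separately for FX006-FX006 and saline-FX006, in place of treatment-versus-control tests.
- Keep change from Day 1, labelled as cumulative change since study entry.

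The cost is wording and extra tables; no new data are needed. The limits should be stated alongside the results. Regression to the mean from the 3-point threshold remains (about 0.15 to 0.36 points with full retention), and waning of the first response can appear as worsening (about 0.6 to 1.4 points with half retention, more with none), which could mask a real effect. Without a concurrent control, neither reference isolates the effect of the second injection.
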